5.0 TREATMENT PLAN

5.1 General

All patients will be registered through CORE. The objective will be to administer AZA or LDAC, and quizartinib at dose level 0 as defined in the Table below. We will first treat 6 patients at dose level -1. If no DLT is identified in >1 patient, this level is defined as MTD and up to 20 patients will be treated at this level with each treatment combination (AC220+ AZA or AC220 + LDAC) for the phase II portion. Other dose levels will be used for dose adjustments for toxicity during therapy.

Approximately 200 patients will be enrolled on this study.

5.2 Schedule

5.2.1 Patients will be treated according to the following schedule:

- AZA will be administered subcutaneously (SQ) or intravenously (IV) for 7 days of every cycle (Days 1-7) as determined by the treating physician. Both SQ and IV forms of administration are FDA approved and considered interchangeable. Patients may start receiving AZA IV and changed to SQ at any time (and vice versa) as needed based on patient and physician preference. AZA is administered in the clinic or chemotherapy administration area.
- Cytarabine will be administered SQ twice daily for 10 days of every cycle (Days 1-10) as determined by the treating physician. Cytarabine can be self-administered by the patient.
- Quizartinib will be administered orally daily for 28 days of every cycle. For the first cycle only, quizartinib will be administered starting on day 5 of the cycle. All subsequent cycles quizartinib will start concomitantly with AZA or cytarabine.

5.2.1.1 The starting and target dose is dose level 1.

Table 1(a): Dose reduction and escalation for Cytarabine + AC220 treatment arm

Dose Level	Cytarabine (mg BID x 10 days)	AC220 (mg/d, uninterrupted)
-3	10	30
-2	15	30
-1	20	30
1 (Starting and target dose)	20	60
2	20	90

Table 1(b): Dose reduction and escalation for AZA+ AC220 treatment arm

Dose Level	AZA (mg/m ² /d x 7 days)	AC220 (mg/d, uninterrupted)
-3	25	30
-2	50	30
-1	75	30
1 (Starting and target dose)	75	60
2	75	90

- 5.2.1.2** Dose reductions beyond those mentioned in this table or different to the doses specified should be discussed with the PI and documentation of the justification recorded in the chart.
- 5.2.2** Patients will be assigned to treatment arm by physician's choice and according to the availability of slots.
- 5.2.2.1** Treatment arm is defined by the use of each of the possible chemotherapy agents (i.e., AZA + AC220 is one treatment arm and Cytarabine + AC220 is another treatment arm).
- 5.2.2.2** Patients in Cohort 2B (FLT3 WT) will only be treated with AZA + AC220. The combination with cytarabine will not be explored in this subset of patients in this study.
- 5.2.3** The first 6 patients on each cohort will receive dose level 1. At least 3 of the patients will be females.
- 5.2.3.1** A cohort is defined by each dose level.
- 5.2.4** Prior to advancing/changing cohorts a cohort summary will be completed and submitted to the Medical Monitor in the IND Office.
- 5.2.5** DLT is defined as any clinically significant non-hematologic adverse event or abnormal laboratory value occurring during the first cycle on study unless the event or laboratory value can clearly be determined to be unrelated to AC220 with the following exceptions:
- CTCAE Grade 3 or 4 AST (SGOT) or ALT (SGPT) that resolves to \leq grade 2 in 14 days
 - Grade 3 nausea, vomiting, or diarrhea that can be managed to \leq grade 2 with standard antiemetic or antidiarrheal medications used at prescribed dose within 7 days of onset.
 - Grade 4 vomiting, or diarrhea that can be managed to \leq grade 3 with standard antiemetic or antidiarrheal medications used at prescribed dose within 48 hours of onset.
 - Grade 3 or 4 electrolyte abnormalities will only be considered DLT if possibly related to study drug and not corrected by optimal replacement therapy within 48 hours.
 - Grade 3 biochemical abnormalities of amylase or lipase without evidence of clinical pancreatitis.
 - Grade 3 anorexia or fatigue.
 - Grade 3 or 4 QTc prolongation will constitute DLT as follows: The QTc interval will be calculated by Fridericia's correction factor (QTcF). If the QTc is > 500 msec the EKG must be evaluated within 2 hours in triplicate and if \geq grade 3 QTc prolongation is confirmed this will be considered a DLT.

Hematologic DLT is defined as grade ≥ 3 neutropenia and/or thrombocytopenia with a hypocellular bone marrow lasting for 6 weeks or more after the start of a course in the absence of residual leukemia (i.e., with less than 5% blasts). Anemia will not be considered for the definition of DLT.

- 5.2.5.1** If DLT occurs in $\geq 2/6$ patients, this dose level would exceed the MTD, and an additional 6 patients will be treated at the next lower dose level. The dose level at which 0-1/6 patients experience DLT (but not higher than 60 mg/day) will be used to treat a maximum of 20 patients in each cohort in the phase II portion of the study. If $\geq 2/6$ patients experience DLT at dose level -1 in any arm, dose level -2 may be explored for that arm(s).
- 5.2.5.2** If DLT is observed in 0 or 1/6 in dose level 1, this cohort will be expanded to treat up to 20 patients in the phase II portion of the study. If $\geq 2/6$ patients experience DLT at dose level 1 for any arm of the study, the dose level at which $\leq 1/6$ patients have experienced DLT will be used for the phase II portion of the study for that arm.
- 5.2.5.3** If DLT is observed in 2/6 patients treated at dose level 1 in any arm, the study will continue at the quizartinib dose of 30 mg PO (dose level -1) for that arm to treat an additional 26 patients at this dose level in the phase II portion of the study.
- 5.2.5.4** Patients that are removed from study before day 28 for any reason other than toxicity and have not experienced DLT will be replaced.
- 5.2.5.5** DLT and MTD will be defined independently for each treatment arm (i.e., AC220 + AZA and AC220 + cytarabine).
- 5.2.6** One cycle of therapy is defined 7 days of AZA or 10 days of LDAC, and 28 days of quizartinib. Patients will receive one cycle of therapy every 4 weeks.
 - 5.2.6.1** Cycles may be started early (but not earlier than day 21) for patients with active disease if judged in the best interest of the patient.
 - 5.2.6.2** Subsequent cycles may be delayed for recovery of toxicity. Delays in start of subsequent cycles greater than 8 weeks should be discussed with the principal investigator.

5.2.6.3 Quizartinib therapy may continue if there is a delay in the start of the next cycle of AZA provided the delay is not due to toxicity possibly related to quizartinib.

5.2.6.4 Subsequent courses may be administered regardless of peripheral blood counts during the first 4 cycles and/or in the presence of residual leukemia. If prolonged myelosuppression (more than 60 days) with evidence of a hypocellular marrow (marrow cellularity less than 5% without evidence of leukemia) is observed subsequent courses of AZA may be given at the next lower dose. If the peripheral counts do not recover (ANC $<1 \times 10^9/L$ and/or platelets $<30 \times 10^9/L$) but there is evidence of residual leukemia in the bone marrow, subsequent cycles can be administered at the discretion of the treating physician not earlier than 3 weeks after the prior cycle.

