5.2.7 Quizartinib Administration

Quizartinib will be administered orally at a starting dose of 60 mg daily for the scheduled 28 days in each cycle.

5.2.7.1 If a dose is missed or vomited, the next dose should not be increased to account for missing a dose. The subject should take the next regular dose at the regularly scheduled time.

5.2.7.2 Treatment may be prolonged beyond the planned 28 days of each cycle if the start of the next cycle of AZA or LDAC is delayed. However, if there are adverse events that mandate treatment interruption or it is considered in the best interest of the patient for safety reasons to interrupt therapy, quizartinib administration can be transiently discontinued and re-started as per guidelines in section 6.0.

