5.3 Duration of Therapy

In the absence of treatment delays due to adverse events, treatment may continue until one of the following criteria applies:

1. Clinically significant progressive disease
2. Grade 4 QTc prolongation.
3. Intercurrent illness that prevents further administration of treatment

4. Patient request
5. General or specific changes in the patient's condition render the patient unacceptable for further treatment in the judgment of the investigator.
6. Unacceptable toxicity that in the opinion of the investigator makes it unsafe to continue therapy. This includes patients with grade 4 non-hematological toxicity unless it reverses to grade ≤ 1 on or before 14 days of interrupting AC220.

5.3.1 It is planned that up to a total of 12 cycles of therapy will be administered for patients deriving benefit from this regimen. Continuation of therapy for patients completing 12 cycles of therapy may be considered on a case by case basis after discussion with the principal investigator.

5.3.2 A minimum of 1 full course (defined as the administration of AZA for 7 days or LDAC for 10 days, and quizartinib for 24 days for cycle one, i.e. days 5-28) will be required for a patient to be considered as having received an adequate trial to evaluate efficacy. All patients receiving at least one dose of any of the two drugs will be considered evaluable for toxicity.

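### Section 5.2.5 ties non-hematologic DLT to the first cycle without fixing the window in days, so a patient who starts cycle 2 early counts as DLT-free after as few as 16 of the planned 24 AC220 days

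*Combined protocol and SAP*

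**What the plan says.** Section 5.2.5 defines non-hematologic DLT as an event or laboratory value of clinical significance "occurring during the first cycle on study unless the event or laboratory value can clearly be determined to be unrelated to AC220", with listed exceptions. Hematologic DLT has its own criterion of 6 weeks or more from the start of a course.

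The length of cycle 1 is governed elsewhere:

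- **Start of AC220 (5.2.1):** "For the first cycle only, quizartinib will be administered starting on day 5 of the cycle".
- **Planned exposure (5.3.2):** "quizartinib for 24 days for cycle one, i.e. days 5-28".
- **Early restart (5.2.6.1):** "Cycles may be started early (but not earlier than day 21) for patients with active disease", if judged to be in the patient's best interest.
- **Delay (5.2.6.2):** "Delays in start of subsequent cycles greater than 8 weeks should be discussed with the principal investigator".
- **AC220 during a delay:** 5.2.6.3 allows it for AZA "provided the delay is not due to toxicity possibly related to quizartinib". Section 5.2.7.2 adds: "Treatment may be prolonged beyond the planned 28 days of each cycle if the start of the next cycle" of AZA or LDAC is delayed.
- **Replacement (5.2.5.4):** "Patients that are removed from study before day 28 for any reason other than toxicity and have not experienced DLT will be replaced".

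Under 5.2.5.1 a dose level exceeds the MTD when 2 or more of 6 patients have a DLT. Section 12.2 uses the same threshold, and 12.3 defines the toxicity monitored in phase II as DLTs.

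**The concern.** The 2-of-6 rule and the 30% toxicity rule in 12.3 treat each patient as one trial with a DLT probability over a common period. An early restart breaks that on one side. Suppose cycle 2 starts on day 21 and a qualifying non-hematologic event occurs on day 24. Read literally, the event belongs to cycle 2 and is not a DLT. The patient has not left the study, so the replacement rule does not apply, and the patient stays in the denominator as DLT-free.

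This situation is foreseeable. Phase I is largely in refractory or relapsed disease (4.1.2), the first on-treatment marrow on day 28 ± 7 days can fall on day 21 (9.2.4), and 5.2.6.4 also allows retreatment of residual leukemia from 3 weeks after the prior cycle. The error has a direction: it makes a dose look more tolerable. At stake are the MTD call in each arm and the sensitivity of the phase II toxicity rule.

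**Working it through.** **1. Exposure days (last day − first day + 1).**

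- Planned: 28 − 5 + 1 = 24, which reproduces the figure in 5.3.2.
- Cycle 2 starts on day 21, so cycle 1 ends on day 20: 20 − 5 + 1 = 16. If day 21 is read as the last day of cycle 1, the count is 17.

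**2. DLT risk over a shortened window.** The documents give no DLT rate for these combinations and no hazard shape, so both are assumptions. With risk p over 24 AC220 days and a constant hazard, the risk over T days is q(T) = 1 − (1 − p)^(T/24). For p = 0.30 and T = 16: q = 1 − 0.7^(2/3) = 0.212.

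**3. Chance of passing the 2-of-6 rule.** With k early starters among six and q = q(16):

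P(at most 1) = (1−q)^k (1−p)^(6−k) + k q (1−q)^(k−1) (1−p)^(6−k) + (6−k) p (1−p)^(5−k) (1−q)^k

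For k = 1 and p = 0.30, the three terms are 0.7884 × 0.1681 = 0.1325, then 0.2116 × 0.1681 = 0.0356, then 5 × 0.3 × 0.2401 × 0.7884 = 0.2839. The sum is 0.452.

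| Risk over 24 days | q(16) | k = 0 | k = 1 | k = 2 | k = 6 |
|---|---|---|---|---|---|
| 0.10 | 0.068 | 0.89 | 0.90 | 0.91 | 0.94 |
| 0.20 | 0.138 | 0.66 | 0.68 | 0.71 | 0.80 |
| 0.30 | 0.212 | 0.42 | 0.45 | 0.49 | 0.63 |

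**4. Front-loaded hazard.** Suppose 80% of the 24-day cumulative hazard falls in the first 8 AC220 days and the rest is even over the next 16. For p = 0.30, H = −ln 0.7 = 0.357, and the 16-day risk is 1 − exp[−(0.8H + 0.2H × 8/16)] = 0.275. P(at most 1/6) is then 0.43, 0.44 and 0.48 for k = 1, 2 and 6, against 0.42 for k = 0.

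**5. Phase II rule, as an outer bound.** Under the constant hazard, a 24-day rate of 40% becomes 1 − 0.6^(2/3) = 0.29 if every patient restarts on day 21. At a response rate of 0.5, the operating characteristics for cohort 2A with AZA (Table 2 in 12.3) give early stopping of 0.694 at 40% toxicity and 0.247 at 30%. The real loss depends on the share of early restarts.

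**6. Which events are exposed.** Scheduled cycle 1 ECGs fall on days 1, 5, 8 and 12, each ± 2 days (9.2.5), so by day 14 at the latest. Section 2.1 reports that QTcF above 500 ms in the first-in-human study arose by Cycle 1 Day 8. Most QTc events are therefore seen inside even the 16-day window. The gap concerns non-hematologic events from day 21 to day 28.

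**The case against.** The strongest reply is that the protocol does imply a 28-day window. Section 5.3.2 places cycle 1 AC220 on days 5-28, 7.1.5 describes a 28-day cycle, 5.2.5.4 sets replacement at day 28, and 6.5.4 requires 28 days of DLT-free follow-up at the next higher level. That shows probable intent, and it stands as a reason to call this an unstated window and not a missing concept. It does not settle the counting: none of these passages says that DLT assessment continues to day 28 once cycle 2 has begun. They are also not fully aligned. Section 5.2.6 defines a cycle by 28 days of quizartinib, and 28 doses from day 5 would end on day 32.

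The reply also says that the effect is small, because early restart is limited to selected patients with active disease and QTc, the expected dose-limiting event, appears early. Both points stand and limit the size.

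A reader might go further and infer that the window can stretch to 52 or 80 AC220 days (56 − 5 + 1 after a 4-week delay, 84 − 5 + 1 after 8 weeks), so that DLT counts are not comparable at all. The documents do not support that. It requires a delay to lengthen cycle 1, whereas 5.2.7.2 can equally be read as dosing after the planned 28 days. Section 5.2.6.2 speaks of delays for recovery from toxicity, and 5.2.6.3 makes continued AC220 conditional on the cause. Eighty days would need a full 8-week delay with uninterrupted AC220. What remains at the long end is an ambiguity to resolve.

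**Conclusion.** The point holds for early restarts. As written, a patient who starts cycle 2 on day 21 has 16 instead of 24 AC220 days at risk, later non-hematologic events up to day 28 are not DLTs, and the patient is not replaced. The bias is toward declaring a dose tolerable and is confined mainly to later-onset non-hematologic events.

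Its size is modest in realistic cohorts. At an assumed 30% risk over 24 days and a constant hazard, the chance of passing rises by about 0.03 to 0.07 with one or two early starters. It would be tempting to quote the rise to 0.63 as the effect, but that needs all six patients to restart on day 21. If most of the risk falls in the first days of dosing, the rise is only 0.01 to 0.02 with one or two early starters. These figures rest on assumed rates and hazard shapes. The gap in the counting rule does not. Because it feeds the MTD decision and the phase II stopping rule and is cheap to close, it should be corrected.

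**What to change.** In 5.2.5, state that non-hematologic DLT is assessed through study day 28 whether or not cycle 2 has started. Use the same window for non-hematologic DLT in 12.2 and 12.3. Leave the 6-week hematologic criterion as it is: a 28-day limit applied to all DLTs in 12.3 would exclude it.

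Also state whether non-hematologic events after day 28 in a delayed cycle 1 count as DLT. Either answer is defensible, but it must be given, and 5.2.5 should be reconciled with 5.2.5.4, 5.2.6, 5.2.7.2 and 6.5.4. Define the window by study day and not also as 24 days from the first AC220 dose: 4.2.8.1 withholds AC220 when the day 5 QTcF is above 450 msec, so the two can differ.

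The cost is a few sentences. Chemistry is already weekly in cycles 1-3 (9.2.3), so no visits are added, and no dosing or cycle-start rule changes. The downside is that a few early-start patients may gain a counted DLT.

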6.2 Toxicity Grading

Toxicity grading will be according to the NCI CTCAE, v4. To prevent unnecessary morbidity, the following guidelines for dose adjustment for drug-related toxicities are recommended.

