6.3 Dose Reductions

Table 2(a): Dose reduction and escalation for Cytarabine + AC220 treatment arm

Dose Level	Cytarabine (mg BID x 10 days)	AC220 (mg/d, uninterrupted)
-3	10	30
-2	15	30
-1	20	30
1 (Starting and target dose)	20	60
2	20	90

Table 2(b): Dose reduction and escalation for AZA+ AC220 treatment arm

Dose Level	AZA (mg/m ² /d x 7 days)	AC220 (mg/d, uninterrupted)
-3	25	30
-2	50	30
-1	75	30
1 (Starting and target dose)	75	60
2	75	90

Dose reductions for non-hematologic toxicity possibly related to study drugs should be performed according to the following table:

Toxicity	Grade	Actions
Non-hematological (excludes myalgia/ arthralgia responding to treatment, inadequately treated nausea, vomiting and diarrhea, or electrolyte abnormalities unless not responding to optimal supplementation)	3	Hold therapy until recovery to Grade \leq 1, then re-start and reduce to the next lower dose level. If toxicity recurs again, hold therapy until recovery to grade \leq 1, then re-start and reduce one additional dose level. Dose reductions below dose level -3 will be considered on an individual basis after discussion with the principal investigator.
Non-hematological, study-drug related	4	Remove from study. An exception can be made if grade 4 toxicity reverses to Grade \leq 1 on or before 14 days of interrupting study drug and re-dosing with AC220 is considered safe and in the best interest of the patient. In those instances treatment may be resumed with a 1 dose-level reduction after discussion with PI and Sponsor.
Non-hematological (excludes myalgia/ arthralgia responding to treatment, inadequately treated vomiting and diarrhea, or electrolyte abnormalities unless not responding to optimal supplementation)	Persistent 2 considered clinically significant or upon patient's request	Hold therapy until recovery to Grade \leq 1, then re-start and reduce to the next lower dose level. If toxicity recurs again, hold therapy until recovery to grade \leq 1, then re-start and reduce one additional dose level. Dose reductions below dose level -3 will be considered on an individual basis after discussion with the principal investigator.
Cardiac Toxicity	QTc > 450 and \leq 480 msec	Check magnesium and potassium levels and correct any abnormalities. If possible, stop any medications that may prolong the QTc interval. Continue quizartinib at the same dose.

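### A cycle-1 grade 4 AST/ALT rise that settles at grade 2 is exempt from DLT in 5.2.5, yet 5.3 and 6.3 call for ending therapy, so a patient who comes off is scored DLT-free

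*Combined protocol and SAP*

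**What the plan says.** **What is exempt from DLT (5.2.5).** Two exceptions cover grade 4 events. The first is "CTCAE Grade 3 or 4 AST (SGOT) or ALT (SGPT) that resolves to" grade 2 or lower in 14 days; the text does not say when those 14 days start. The second is "Grade 4 vomiting, or diarrhea that can be managed to" grade 3 or lower within 48 hours. A separate exception covers "Grade 3 nausea, vomiting, or diarrhea that can be managed to" grade 2 or lower within 7 days of onset.

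**What ends therapy.** Section 5.3 item 6 names "Unacceptable toxicity that in the opinion of the investigator makes it unsafe to continue therapy" and adds: "This includes patients with grade 4 non-hematological toxicity unless it reverses to grade" 1 or lower within 14 days of interrupting AC220. In the 6.3 table, the row for drug-related grade 4 non-hematologic toxicity reads "Remove from study. An exception can be made if grade 4 toxicity reverses to Grade" 1 or lower in the same window. Unlike the grade 3 and persistent grade 2 rows, this row has no carve-outs.

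**How such a patient is counted.** Section 5.2.5.4 replaces only patients removed before day 28 for reasons other than toxicity. Section 5.3.2 keeps anyone who received a dose evaluable for toxicity. Section 12.3.2 defines the monitored toxicity as DLTs. Sections 5.2.5.1 and 12.2 accept a dose level with at most 1 DLT in 6 patients.

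**The concern.** The recovery threshold for escaping a DLT (grade 2) is looser than the one for staying on treatment (grade 1). Between them lies a patient whose treatment is stopped for good because of drug toxicity in cycle 1, but who adds nothing to the DLT count. No single sentence says this; it follows from reading the sections together.

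Two decisions depend on that count. In phase I, one such patient plus one counted DLT is scored 1/6 and the level is accepted; counting both gives 2/6, which exceeds the MTD. In phase II the toxicity stopping boundaries use the same count. Leaving events out of the numerator while keeping the patients in the denominator can only move both decisions toward accepting the dose.

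**Working it through.** **1. Tracing one patient (AST/ALT route).** AC220 starts on day 5. ALT reaches grade 4 on day 10 and AC220 is stopped that day. The 14-day window closes on day 10 + 14 = 24, with ALT at grade 2.

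| Section | Test | Result |
|---|---|---|
| 5.2.5 | Grade 2 or lower in 14 days? | Yes, so not a DLT |
| 5.3 item 6 and 6.3 | Grade 1 or lower within 14 days of interruption? | No, so the text calls for ending therapy |
| 5.2.5.4 | Removed for a reason other than toxicity? | No, so not replaced |
| 5.3.2 | Received a dose? | Yes, so in the denominator |
| 12.3.2 | DLT? | No, so counted as free of toxicity |

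**2. Vomiting/diarrhea route.** This is narrower. Grade 4 must be controlled to grade 3 or lower within 48 hours, and the grade 3 exception then requires grade 2 or lower within 7 days. Only an event that stays at grade 2 beyond 14 days off AC220 falls in the gap.

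**3. Reproducing the plan's phase II rule.** The inputs from 12.3 are a beta(0.6, 1.4) prior and stopping if Pr(θ > 0.30 | data) > 0.9. With x DLTs in n patients the posterior is beta(0.6 + x, 1.4 + n − x). This reproduces all seven boundaries printed for the AZA groups: 8/15, 9/20, 11/25, 13/30, 15/35, 16/40 and 18/45. At 15 patients, for example, 7 DLTs give 0.893 and 8 give 0.960.

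An exact recursion over these looks up to 50 patients, with the toxicity boundaries alone, can be checked against protocol Table 2 at response rate 0.65, where futility stopping is negligible:

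| Toxicity rate | Stop probability: computed / Table 2 | Average N: computed / Table 2 |
|---|---|---|
| 0.3 | 0.203 / 0.204 | 44.85 / 44.8 |
| 0.4 | 0.676 / 0.676 | 32.4 / 32.4 |

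**4. Illustrating the size.** The documents give no rate for these events. I assume they affect 0.5 to 2 percentage points of patients.

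Phase I: P(accept) = P(X ≤ 1) = (1 − p)^6 + 6p(1 − p)^5. At p = 0.10 this is 0.5314 + 0.3543 = 0.886.

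| Counted DLT rate | As written | 0.5 points added | 2 points added |
|---|---|---|---|
| 10% | 0.886 | 0.876 (p = 0.105) | 0.844 (p = 0.12) |
| 20% | 0.655 | 0.643 (p = 0.205) | 0.606 (p = 0.22) |

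Phase II, AZA group of 50: probability of stopping on the toxicity boundaries alone, where total toxicity means DLTs plus the exempt events.

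| Total toxicity | All counted | 0.5 points uncounted | 2 points uncounted |
|---|---|---|---|
| 20% | 0.015 | 0.012 (p = 0.195) | 0.007 (p = 0.18) |
| 30% | 0.203 | 0.185 (p = 0.295) | 0.137 (p = 0.28) |

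**The case against.** **The thresholds have different jobs.** Section 5.2.5 decides what limits a dose; 5.3 and 6.3 protect the individual patient. A stricter threshold for re-dosing than for scoring a DLT is coherent, and the transaminase exemption looks deliberate. This stands. A reader might infer that the protocol contradicts itself, but nothing in it says the thresholds must match. What remains is narrower: no text says how to score a patient whose treatment actually ends this way.

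**Removal is not automatic.** Item 6 refers to the investigator's opinion, 6.2 says that "the following guidelines for dose adjustment for drug-related toxicities are recommended", and 6.3.3 allows other modifications after discussion with the PI. The clocks may also differ, since 5.3 and 6.3 count from interruption of AC220. All this lowers the number of patients affected. It does not change the scoring of one who comes off.

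**The event stays visible.** It remains in the safety data, and the cohort summary under 5.2.4 may show it to the Medical Monitor. The decision rules still count only DLTs.

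**The size is assumed.** This also stands. The 30% limit is set for the DLT rate as the protocol defines it. The 30% row above applies it to a broader endpoint, so the row is an illustration and does not show that the rule fails its stated aim.

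**Residual grade 3.** A reader might infer that vomiting or diarrhea lingering at grade 3 also escapes. It does not: beyond 7 days it falls outside the grade 3 exception and is a DLT.

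**Conclusion.** The gap is real on the current text and is minor. A patient taken off treatment in cycle 1 because a drug-related grade 4 AST/ALT rise (or, rarely, grade 4 vomiting or diarrhea) stalled at grade 2 is scored DLT-free, and the error runs only toward accepting the dose. I am confident of the textual reading. The consequence is less certain, because it depends on how often such events occur and how often discretion keeps the patient on treatment.

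Under the assumed 0.5 to 2 points, the chance of accepting a phase I level is overstated by about 0.010 to 0.042 at a 10% counted DLT rate (0.886 − 0.876; 0.886 − 0.844) and by 0.012 to 0.049 at 20% (0.655 − 0.643; 0.655 − 0.606). A reader might infer that dose selection or safety monitoring is seriously compromised; without an event rate the documents do not support that.

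**What to change.** Add one sentence to 5.2.5: a cycle-1 grade 4 non-hematologic event that is not clearly unrelated to AC220 counts as a DLT, despite the AST/ALT and vomiting/diarrhea exceptions, if therapy is permanently discontinued because the event did not reverse to grade 1 or lower (or to the baseline grade, if that was higher) within 14 days of interrupting AC220, including when that window closes after day 28.

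The limits in that sentence matter:

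- **Grade 4 only.** Item 6 opens with a criterion that has no grade floor. Counting every discontinuation under it would make exempt grade 3 fatigue or anorexia a DLT whenever the investigator chose to stop. The grade 3 exceptions stay as they are.
- **Baseline allowance.** Section 4.1.4.2 admits ALT up to 5 times ULN with suspected liver infiltration. Such a patient might return to baseline and still miss grade 1.
- **Existing limits kept.** The 48-hour and 7-day limits for vomiting and diarrhea stay unchanged.

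The cost is an amendment with no new visits or data. The counted DLT rate rises slightly, and scoring depends to some extent on the decision to discontinue. For onset and drug stop on day 28, the call may wait until day 28 + 14 = 42. For AST/ALT with the drug stopped at onset, that is no longer than the 14 days the exception already needs, and the hematologic DLT already requires cytopenia "lasting for 6 weeks or more after the start of a course". For vomiting and diarrhea the wait can grow from 48 hours or 7 days to 14 days.

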6.5 Inpatient Dose Escalation for Patients Treated at Dose Level -1 or Lower

Inpatient dose escalation will be permitted for these patients provided:

- 6.5.1** Patient has completed ≥ 1 cycle at dose level -1 or lower, and
- 6.5.2** Patient has not experienced any grade 3 or higher non-hematologic toxicity, and
- 6.5.3** Patient has not experienced hematologic DLT, and
- 6.5.4** At least 3 patients have been treated at the next higher dose level and followed for at least 28 days without experiencing DLT.
- 6.5.5** Patients who have experienced no QTc prolongation above 480 msec in whom optimal anti-leukemia effect has not been reached may have the dose of quizartinib increased to by one dose level. Patients who have such dose escalation will have an EKG done 24 hours and 7 days after dose escalation. No dose escalation above 90 mg/day will be allowed.
- 6.5.6** Because of the increased risk of QTc prolongation in women treated at doses > 90 mg/day in prior studies with AC220, dose escalation above 90 mg/day is not allowed in women.

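### Hematologic DLT cannot be met before day 42, but replacement stops at day 28 and no minimum follow-up precedes the 6-patient dose decision

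*Combined protocol and SAP*

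**What the plan says.** All references are to the combined protocol and SAP.

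- **DLT definition (5.2.5).** Non-hematologic DLTs are those "occurring during the first cycle on study". The hematologic definition is a separate sentence with no cycle limit. It requires grade 3 or worse neutropenia and/or thrombocytopenia, a hypocellular marrow, fewer than 5% blasts, and persistence "lasting for 6 weeks or more after the start of a course".
- **Replacement (5.2.5.4).** "Patients that are removed from study before day 28 for any reason other than toxicity and have not experienced DLT will be replaced".
- **Cohort decision (5.2.5.1 to 5.2.5.3, 12.2).** With 0 or 1 DLT in 6 the dose level passes; with 2 or more it exceeds the MTD and the next lower level is used. Section 5.2.4 asks for a cohort summary to the Medical Monitor before cohorts change. None of these sections gives a minimum follow-up.
- **Timing of course 2 (5.2.6).** "Patients will receive one cycle of therapy every 4 weeks". Section 5.2.6.1 allows a start from day 21 for active disease. Section 5.2.6.4 adds: "Subsequent courses may be administered regardless of peripheral blood counts during the first 4 cycles".
- **Within-patient escalation (6.5.4).** One condition is: "At least 3 patients have been treated at the next higher dose level and followed for at least 28 days without experiencing DLT".

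**The concern.** The definition and the rules around it run on different clocks. One component of the DLT takes six weeks to mature, while the rule that decides who stays in the denominator stops at four. A patient can therefore be kept as one of the 6, scored as having no DLT, although one of the two ways of having a DLT was never open to observation.

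The 6-patient count decides whether a treatment arm stays at dose level 1 or steps down, and it does so separately for the AZA and LDAC arms. With a threshold of 2 in 6, one uncounted event can reverse the result. An unobserved component can only lower the count, so any error favors staying at the starting dose. Prolonged marrow suppression also matters for this regimen: section 2.1 names bone marrow as a principal target organ of quizartinib toxicity, and the partner drugs are cytotoxic.

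**Working it through.** **The plan's own figures.** The plan gives no operating characteristics for the 6-patient rule. Its only calculated figures that rest on a DLT count are the phase II toxicity boundaries in 12.3. For the AZA groups, with a beta(0.6, 1.4) prior and a stop when Pr(rate > 0.30 | data) > 0.9:

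- 8 of 15: posterior beta(8.6, 8.4), probability 0.960, stop.
- 7 of 15: posterior beta(7.6, 9.4), probability 0.893, continue.

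This gives the printed 8/15, and the remaining boundaries up to 18/45 also reproduce. The boundaries are not in question; the completeness of the count is.

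**Timing.** Six weeks is 6 × 7 = 42 days. The replacement cut-off is day 28, a gap of 42 − 28 = 14 days. By definition, no hematologic DLT can have been met at day 28.

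**Who falls into the gap.** The definition excludes residual leukemia. A patient leaving on days 28-41 with persistent leukemia could not have met it at that point, and one whose counts have recovered is also settled. What remains is the patient with cleared leukemia, continuing grade 3 or worse cytopenia, and an exit in that 14-day window. Section 5.2.5.4 does not replace that patient.

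**Overlap with course 2.** A course begun at about day 29 puts some 13 days of further therapy before day 42. Section 9.2.2 schedules weekly blood counts through cycle 3, so counts near day 42 should exist for patients still on study. Section 9.2.4 places the marrow at day 28 ± 7 and then every 1-3 cycles, with none fixed near day 42. The definition says only that the clock starts with a course, and no rule says how cytopenia at day 42 is attributed once two courses have begun.

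**Size, under assumptions.** The documents give no DLT rate for either component. Assume a non-hematologic rate q of 0.10-0.15 and an independent hematologic rate h of 0.10-0.20 per patient.

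- Total rate: p = 1 − (1 − q)(1 − h).
- Chance of 2 or more in 6: 1 − (1 − p)^6 − 6p(1 − p)^5.
- If no hematologic DLT is captured, use q in place of p.
- If exactly one of the 6 has the hematologic part unobserved: 1 − (1 − p)^5(1 − q) − [q(1 − p)^5 + 5p(1 − p)^4(1 − q)].

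| q | h | p | All captured | One of 6 unobserved | None captured |
|---|---|---|---|---|---|
| 0.10 | 0.10 | 0.190 | 0.320 | 0.283 | 0.114 |
| 0.10 | 0.20 | 0.280 | 0.536 | 0.468 | 0.114 |
| 0.15 | 0.10 | 0.235 | 0.430 | 0.396 | 0.224 |
| 0.15 | 0.20 | 0.320 | 0.622 | 0.564 | 0.224 |

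First row, all captured: 1 − 0.2824 − 6 × 0.19 × 0.3487 = 0.320. Last row: 1 − 0.0989 − 6 × 0.32 × 0.1454 = 0.622.

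The last column is the extreme case. The one-patient column is closer to what 5.2.5.4 produces, but it gives the leaving patient the average rate h. A patient who already has unresolved cytopenia and cleared leukemia would be at higher risk than that.

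**The case against.** The best defense is that nothing in the text requires scoring at day 28.

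- The first-cycle limit applies to non-hematologic events only. A hematologic DLT reached at day 42 counts, and a careful team could wait for it before completing the cohort summary. This stands. A reader might infer that the protocol takes the cohort decision at day 28; no section says so. The fault is that no follow-up is required at all.
- A reader might take 6.5.4 as proof of premature MTD decisions. It governs escalation in individual patients at level -1 or lower and sets neither the MTD nor the phase II dose. Its 28 days still sit badly with a six-week definition, but that is a separate inconsistency.
- A reader might count the day-21 start as lost observation. It is open only to patients with active disease, who cannot meet the hematologic definition while leukemia persists.
- Starting course 2 regardless of counts is permitted, not required. Sections 5.2.6.2 and 6.4.1.3 allow delay or holding. This stands, and it leaves attribution, rather than missing counts, as the problem for patients who stay on study.
- A general upward bias in the MTD might be inferred. Section 5.2.5.1 caps the phase II dose at 60 mg/day, the starting level, so under that section the exposure is a missed step down. Section 12.2 still describes a move to level 2; that conflict is a separate point.
- Phase I patients at the chosen dose enter the phase II DLT monitoring in 12.3, so a late event can still be counted there. This helps for patients who remain under observation, but not for one who left on days 28-41.

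**Conclusion.** The point holds in a limited form. The six-week definition and the day-28 replacement rule conflict as written. A patient with cleared leukemia and unresolved grade 3 or worse cytopenia who leaves on days 28-41 is kept as DLT-free with the hematologic component unobserved. The absence of a minimum follow-up before the cohort decision, and of an attribution rule when course 2 has started, leaves the same component open for other patients.

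The 14-day gap follows from the text alone; the effect on the dose decision does not. The contrast of 0.32-0.62 against 0.11-0.22 is an upper bound that rests on assumed, independent rates and on no hematologic DLT ever being captured, which the documents do not imply. If one patient in 6 is affected, the same assumptions lower the chance of 2 or more DLTs by about 0.03 to 0.07. The direction is toward failing to step down from the starting dose. The change should be made, but nothing here shows that a wrong dose would be chosen.

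**What to change.** 1. In 5.2.5, define a phase I patient as DLT-evaluable after a DLT, or at day 42 without one, or earlier if counts have recovered or residual leukemia is documented. The earlier route should apply only once the first-cycle window for non-hematologic DLT is complete.
2. Align 5.2.5.4 with that definition, so that non-DLT patients who leave before becoming evaluable are replaced. Keep its existing exception for removal for toxicity, and say how such patients are counted.
3. In 5.2.5.1 to 5.2.5.3 and 12.2, state that the 0-1/6 versus 2-or-more/6 decision is taken only when all 6 patients are evaluable.
4. State which course start the six weeks run from, and how cytopenia at day 42 is attributed when course 2 has already begun.
5. Separately, the sponsor must reconcile the 28-day condition in 6.5.4 with the six-week hematologic definition.

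The cost is amendment wording, up to two more weeks per 6-patient cohort, and possibly some replacements. Letting recovered counts or documented residual leukemia settle the hematologic part early limits the replacements to patients whose status is truly unknown.
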